Target lesions. All measurable lesions up to a maximum of 2 lesions per organ and 5 lesions in total, representative of all involved organs, should be identified as **target lesions** and recorded and measured at baseline. Target lesions should be selected on the basis of their size (lesions with the longest diameter), be representative of all involved organs, but in addition should be those that lend themselves to reproducible repeated measurements. It may be the case that, on occasion, the largest lesion does not lend itself to reproducible measurement in which circumstance the next largest lesion which can be measured reproducibly should be selected. A sum of the diameters (longest for non-nodal lesions, short axis for nodal lesions) for all target lesions will be calculated and reported as the baseline sum diameters. If lymph nodes are to be included in the sum, then only the short axis is added into the sum. The baseline sum diameters will be used as reference to further characterize any objective tumor regression in the measurable dimension of the disease.

Non-target lesions. All other lesions (or sites of disease) including any measurable lesions over and above the 5 target lesions should be identified as **non-target lesions** and should also be recorded at baseline. Measurements of these lesions are not required, but the presence, absence, or in rare cases unequivocal progression of each should be noted throughout follow-up.

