### 10.1.3 Methods for Evaluation of Measurable Disease

All measurements should be taken and recorded in metric notation using a ruler or calipers. All baseline evaluations should be performed as closely as possible to the beginning of treatment and never more than 4 weeks before the beginning of the treatment.

The same method of assessment and the same technique should be used to characterize each identified and reported lesion at baseline and during follow-up. Imaging-based evaluation is preferred to evaluation by clinical examination unless the lesion(s) being followed cannot be imaged but are assessable by clinical exam.

Clinical lesions Clinical lesions will only be considered measurable when they are superficial (e.g., skin nodules and palpable lymph nodes) and  $\geq 10$  mm diameter as assessed using calipers (e.g., skin nodules). In the case of skin lesions, documentation by color photography, including a ruler to estimate the size of the lesion, is recommended.

Chest x-ray Lesions on chest x-ray are acceptable as measurable lesions when they are clearly defined and surrounded by aerated lung. However, CT is preferable.

Conventional CT and MRI This guideline has defined measurability of lesions on CT scan based on the assumption that CT slice thickness is 5 mm or less. If CT scans have slice thickness greater than 5 mm, the minimum size for a measurable lesion should be twice the slice thickness. MRI is also acceptable in certain situations (e.g. for body scans).

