#### 10.1.4 Response Criteria

##### 10.1.4.1 Evaluation of Target Lesions

|                                  |   |
|----------------------------------|---|
| Complete Response (CR):   | Disappearance of all target lesions. Any pathological lymph nodes (whether target or non-target) must have reduction in short axis to <10 mm.   |
| Partial Response (PR):    | At least a 30% decrease in the sum of the diameters of target lesions, taking as reference the baseline sum diameters   |
| Progressive Disease (PD): | At least a 20% increase in the sum of the diameters of target lesions, taking as reference the smallest sum on study (this includes the baseline sum if that is the smallest on study). In addition to the relative increase of 20%, the sum must also demonstrate an absolute increase of at least 5 mm. (Note: the appearance of one or more new lesions is also considered |

progressions).

Stable Disease (SD): Neither sufficient shrinkage to qualify for PR nor sufficient increase to qualify for PD, taking as reference the smallest sum diameters while on study

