#### 12.1.2 Study Endpoints:

The primary endpoint is objective response based on RECIST 1.1 criteria. Response criteria and categories are defined in detail in Sections [10.1.1-10.1.4](#).

Secondary endpoints include toxicity, time to response (TTR), response duration (RD), progression free survival (PFS), and overall survival (OS). Definition, assessment, and reporting of toxicity (adverse events) may be found in Sections [6.1](#), or [10](#). TTR, RD, PFS, and OS are defined in Sections [10.2.1](#), [10.1.5](#), [10.1.6](#), and [10.2.2](#), respectively.

Exploratory endpoints include metabolic response by PET/CT scan, and several laboratory biomarkers listed in [Section 1.3](#) (Exploratory Objectives), and described in [Section 8](#) and in the [Appendix D](#).

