## **2. Tumor Response Evaluation According To RECIST**

### **2.1 Image Acquisition**

Response assessment using RECIST criteria will be performed on all CT scans during the trial. Scans will be performed after administration of oral and IV contrast agents according to institutional practices.

Iodinated intravenous (IV) contrast media may be administered for diagnostic CT scans per standard institutional practice, unless contraindicated. The decision not to use IV contrast for CT is at the discretion of the performing radiologist. If IV contrast is *not* administered for these scans, then these non-contrast CT series can be used for both RECIST and volumetric measurements by prospectively reconstructing the image data into both thick (2.5 to 5 mm) and thin-section (1 to 1.25 mm) series, respectively..

The CT scan with contrast is obtained with arms elevated above the head and at suspended maximal inspiration to provide optimal relative contrast of lung lesions within aerated lung. Typical parameters for image acquisition and reconstruction are shown in Table 2.

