## 2.2 Image Data Analysis

**2.2.1** The following categories of disease will be used in determining response to treatment by RECIST:

- **Measurable disease:** The presence of at least one measurable lesion. If the measurable disease is restricted to a solitary lesion, its neoplastic nature should be confirmed by cytology | histology.
- **Measurable lesions:** Lesions that can be accurately measured in at least one dimension with longest diameter  $\geq 10$  mm with helical CT.
- **Non-measurable lesions:** all other lesions, including small lesions (longest diameter  $< 20$  mm with conventional techniques or  $< 10$  mm with helical CT scan), i.e., bone lesions, leptomeningeal disease, Ascites, pleural/pericardial effusion, inflammatory breast disease, lymphangitic cutis | pulmonis, cystic lesions, and also abdominal masses that are not confirmed and followed by imaging techniques.

All measurements will be taken and recorded in metric notation on a calibrated diagnostic imaging workstation at full resolution using electronic calipers. The baseline measurements will be performed within one week of the start of treatment; measurements obtained following chemotherapy cycles will be obtained on scans performed within 1-3 days of the next cycle of treatment. The same method of assessment and the same technique will be used to characterize each identified and reported lesion at baseline and during follow-up. Lung lesions will be

evaluated on lung windows; mediastinal and or soft tissue lesions will be evaluated on soft tissue windows. The acquisition parameters provided above serve as guidelines for CT technique.

“Target” and “Non-Target” lesions will be documented according to the following guidelines:

- All measurable lesions up to a maximum of five lesions per organ and 10 lesions total, representative of all involved organs, should be identified as **target lesions** and recorded and measured at baseline.
- Target lesions should be selected on the basis of their size (lesions with the longest diameter and their suitability for accurate repeated measurements.
- A sum of the longest diameter (LD) for all target lesions will be calculated and reported as the baseline sum LD. The baseline sum LD will be used as reference by which to characterize the objective tumor response.

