**Confirmation:**

- To be assigned the status of PR or CR, changes in tumor measurements must be confirmed by repeat assessments that should be performed no less than 4 weeks after the criteria for response are first met. Longer intervals as determined by the study protocol may also be appropriate.
- To be assigned the status of SD, follow-up measurements must have met the SD criteria at least once after study entry at a minimum interval (in general, not less than 6-8 weeks) that is defined in the study protocol.

**Duration of Overall Response:** This is measured from the time measurement criteria are met for CR or PR (whichever status is recorded first) until the first date that recurrence or PD is objectively documented, taking as reference for PD the smallest measurements recorded since the treatment started.

**Duration of Stable Disease:** Stable disease is measured from the start of the treatment until the criteria for disease progression are met, taking as reference the smallest measurements recorded since the treatment started. The clinical relevance of the duration of SD varies for different tumor types and grades.

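### Appendix C section 2.2 gives CT readers response rules that contradict the RECIST 1.1 rules of Section 10, on which the primary endpoint rests

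*Combined protocol and SAP*

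**What the plan says.** Section 12.1.2 states: "The primary endpoint is objective response based on RECIST 1.1 criteria". It takes the response criteria from Sections 10.1.1 to 10.1.4, response duration from 10.1.5 and PFS from 10.1.6. Section 12.4 takes stable disease duration from 10.1.5.

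Section 10.1.2 sets the target lesions: "All measurable lesions up to a maximum of 2 lesions per organ and 5 lesions in total". Nodes enter the sum by short axis and are measurable from 15 mm short axis. Cystic metastases may count as measurable. For progression, Section 10.1.4.1 requires a 20% increase and adds that "the sum must also demonstrate an absolute increase of at least 5 mm".

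Appendix C section 2.2 sets a second list of disease categories, target limits and response tables. Its target rule is "All measurable lesions up to a maximum of five lesions per organ and 10 lesions total". The preceding section of the appendix gives it wide scope: "Response assessment using RECIST criteria will be performed on all CT scans during the trial".

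Section 10.3 plans a review by an outside radiologist before stage 2 and at completion. It does not say which lesion-selection rules that reader applies.

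**The concern.** Response is a reader's classification, and target lesions are fixed at baseline by readers at several institutions. Appendix C is where a reader looks for CT instructions. A site that follows it and a site that follows Section 10 can choose different lesions and measure nodes on different axes. They can then report different categories for the same scans, each in line with the document.

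At stake are the primary endpoint, PFS, response duration and stable disease duration. The exploratory volumetric comparison in Appendix I is also affected, because it reuses the pre-specified target lesions and their RECIST results.

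**Working it through.** **1. The two rule sets side by side**

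| Item | Section 10 | Appendix C section 2.2 |
|---|---|---|
| Target cap | 2 per organ, 5 total | 5 per organ, 10 total |
| Nodes in the sum | short axis only | longest diameter, no nodal exception |
| Nodal threshold | 15 mm short axis | none |
| Cystic metastases | may be measurable | cystic lesions listed as non-measurable |
| PR | 30% decrease in the sum | 30% decrease in the sum of longest diameters |
| PD (target lesions) | 20% increase and at least 5 mm | 20% increase only |

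**2. Can the same scans give different response categories?** The measurements below are invented; they are not trial data. New lesions and non-target progression are assumed absent, and any response is assumed confirmed.

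- Five lung lesions of 25, 15, 10, 10 and 10 mm. The two largest go from 40 to 26 mm in sum, the other three from 30 to 27 mm.
  - Section 10 (two targets): (26 - 40)/40 = -35.0%, PR.
  - Appendix C (five targets): (53 - 70)/70 = -24.3%, SD.
- Reverse case: 30, 28, 26, 24 and 22 mm become 24, 22, 15, 13 and 12 mm.
  - Section 10: (46 - 58)/58 = -20.7%, SD.
  - Appendix C: (86 - 130)/130 = -33.8%, PR.
- One node, short axis 20 to 13 mm, long axis 30 to 24 mm.
  - Section 10: -7/20 = -35%, PR.
  - Appendix C: -6/30 = -20%, SD.

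The disagreement therefore runs in both directions.

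**3. The 5 mm rule.** Let S be the smallest sum on study. Appendix C calls progression at an increase of 0.20 × S; Section 10 also needs 5 mm. The rules differ for increases from 0.20 × S up to just under 5 mm. That range exists only if 0.20 × S < 5, that is S < 25 mm. Example: 20 to 24 mm is +20% but +4 mm, so PD under Appendix C and SD under Section 10.

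**4. The design figures.** Section 12.1.1 gives p0 = 5%, p1 = 20%, 12 patients in stage 1 (continue with at least 1 responder), 29 in total (promising with at least 3), significance level 0.15, power 0.90, and early-termination probability 0.540 under the null.

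- Early termination at p0: 0.95^12 = 0.540.
- P(promising) = sum over x = 1 to 12 of P(X = x) × P(Y ≥ max(0, 3 - x)), with X ~ Bin(12, p) and Y ~ Bin(17, p). Result: 0.148 at p0 and 0.9005 at p1.

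The stated design is reproduced.

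**5. When does one reclassified responder matter?**

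- Stage 1: 0 versus 1 of 12. The chance of exactly 1 is 12 × p × (1 - p)^11 = 0.341 at 5% and 0.206 at 20%.
- Final analysis: 2 versus 3 of 29. The chance of passing stage 1 and ending with exactly 2 or 3 is 0.169 + 0.098 = 0.267 at 5%, and 0.026 + 0.072 = 0.098 at 20%.

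**6. Range for an assumed net shift in the observed response rate.** The documents give no rate of disagreement.

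| Assumed shift (points) | P(promising), p0 shifted up | Power, p1 shifted down |
|---|---|---|
| 0 | 0.148 | 0.901 |
| 1 | 0.214 | 0.881 |
| 2 | 0.285 | 0.858 |
| 3 | 0.357 | 0.831 |
| 5 | 0.498 | 0.763 |

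**The case against.** The best reply is that the governing text is already named. Sections 12.1.2 and 12.4 assign response, response duration, PFS and stable disease duration to Section 10, and the objectives name RECIST 1.1. The body of the protocol points CT readers to Appendix C only in Section 2.3, for PET/CT data, and PET/CT is optional. This stands as far as it goes: the endpoint definition is not open, and a careful statistician would infer that Section 10 governs. It does not dispose of the point. Appendix C itself extends RECIST assessment to every CT scan in the trial, and no sentence withdraws its rules or states precedence.

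Several stronger readings are tempting and are not supported:

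- *Appendix C sets a longer minimum for stable disease.* Its interval is "in general, not less than 6-8 weeks", but the same sentence leaves the value to the study protocol, and Section 10.1.4.3 sets at least 4 weeks. That is deferral, not contradiction.
- *Section 10.1.3 conflicts with the imaging calendar.* Its limit, "never more than 4 weeks before the beginning of the treatment", is an outer bound that days -14 to -1 satisfy. The real mismatch is with Appendix C: "The baseline measurements will be performed within one week of the start of treatment". A scan on day -12 meets the Schema and calendar footnote c but not the appendix. This mismatch is not shown to change any response category.
- *The missing 5 mm rule turns PR into SD.* It separates PD from SD. It reaches response only indirectly, by closing the best-response window before a later response.
- *Any one reclassified patient decides the trial.* This is true only at the boundaries in step 5 of the working.
- *The lung is where the caps differ most.* The caps are the same for every organ. Section 2.1 says only that distant spread to the lung in particular is not uncommon.

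**Conclusion.** The concern holds as an internal contradiction that reaches the primary endpoint. The target caps and the nodal axis can move a patient between PR and SD in either direction. The missing 5 mm minimum can move a patient from SD to PD when the smallest sum is under 25 mm, which affects PFS and the duration endpoints.

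Its size in practice is unknown. The lesion measurements are invented and the shifts in the response rate are assumptions. What is firm is that the decision rules rest on 1 of 12 and 3 of 29. If one responder is reclassified, the final conclusion is exposed with probability about 0.27 at a 5% response rate and 0.10 at 20%, counting outcomes of exactly 2 or 3 responders after stage 1 is passed.

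A reader might infer that reported responses were in fact misclassified. Section 8 and Appendix D mention two partial responses, but neither says which target rules were used or that two is the final count, so the documents do not support that inference. The stated design figures are correct and do not change.

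**What to change.** - State in Section 10 and at the head of Appendix C that Section 10.1 (RECIST 1.1) alone governs all response and progression calls, by the sites and by the outside radiologist of Section 10.3.
- In Appendix C section 2.2, delete or align the text on lesion categories, target caps, sums of longest diameters and the response tables. Keep the acquisition parameters and the harmless reading instructions (lung and soft-tissue windows, electronic calipers), so do not strike the whole section.
- Reconcile the one-week baseline measurement window in Appendix C with days -14 to -1 in the Schema and calendar footnote c.
- At the planned outside read, select targets and measure nodes by Section 10. Where a node was recorded by longest diameter, its short axis must be measured anew; re-summing the existing measurements is not enough.

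The cost is an appendix edit plus the extra nodal measurements within a read that is already planned. Sample size, decision rules and error rates stay as they are.

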**Confirmation:**

- To be assigned the status of PR or CR, changes in tumor measurements must be confirmed by repeat assessments that should be performed no less than 4 weeks after the criteria for response are first met. Longer intervals as determined by the study protocol may also be appropriate.
- To be assigned the status of SD, follow-up measurements must have met the SD criteria at least once after study entry at a minimum interval (in general, not less than 6-8 weeks) that is defined in the study protocol.

**Duration of Overall Response:** This is measured from the time measurement criteria are met for CR or PR (whichever status is recorded first) until the first date that recurrence or PD is objectively documented, taking as reference for PD the smallest measurements recorded since the treatment started.

**Duration of Stable Disease:** Stable disease is measured from the start of the treatment until the criteria for disease progression are met, taking as reference the smallest measurements recorded since the treatment started. The clinical relevance of the duration of SD varies for different tumor types and grades.

### **Specific Aims**

The fundamental hypothesis of our study is that distinct genomic aberrations including amplifications, mutations, and gene translocations that target specific genes and signaling pathways will distinguish those tumors that had a meaningful response to SAHA. We propose that our comprehensive study of the genomic landscape of this patient population, specifically looking at the differences in therapeutic benefit, will provide a unique data set that can be exploited for advancing effective targeted therapy for patients with disease. To accomplish our study we will complete the following Aims:

## SPECIFIC AIMS

- Flow sort diploid, aneuploid, and tetraploid populations of tumor cells from FFPE tissue blocks from each of 5 patients who benefited from SAHA therapy and from each of 5 patients who did not demonstrate a durable benefit.
- Profile the genomes of each cell population using oligonucleotide CGH arrays. This will confirm the identification of tumor populations in each sample and provide genomic landmarks for NGS analysis.
- Perform whole exome analysis of the sorted tumor population and matching germ line sample for each of the 10 patients. The combined aCGH and exome data will be mined to identify genes and pathways that are targeted by select somatic events in each of the patient subsets.

**Methods** *FFPE Sample Preparation and Flow Sorting:* Excess paraffin is removed with a scalpel from individual 40-60µm scrolls which are then washed with 1ml Xylene for 5 minutes to remove remaining paraffin. Each sample is rehydrated in sequential ethanol washes (100% 5 minutes x2, then 95%, 70%, 50% and 30% ethanol) and washed 2 times in 1ml 1mM EDTA pH 8.0. A 1ml aliquot of 1mM EDTA pH 8.0 is added to the samples which are then incubated at 95°C for 80 minutes to facilitate the removal of protein cross-links. Samples are cooled to room temperature for ≥ 5 minutes, followed by addition of 300µl PBS 7.4 and gentle centrifugation for 2 minutes. The pellet is washed 3 times with 1ml PBS 7.4/0.5mM CaCl2 to remove EDTA. Each sample is digested overnight (6-17 hours) in 1ml of enzymatic cocktail containing 50 units/ml of collagenase type 3, 80 units/ml of purified collagenase, and 100 units/ml of hyaluronidase in PBS pH 7.4/0.5mM CaCl2 buffer. Following overnight digestion 500µl NST buffer is added and samples are centrifuged for 5 minutes at 3000rcf, after which pellets are resuspended in 750µl of NST/10% fetal bovine serum and then passed through a 25g needle 10-20 times. The samples are filtered through a 35µm mesh and collected into a 5ml polypropylene round bottom tube. The mesh is rinsed with an additional 750µl of NST/10% fetal bovine serum and placed on ice while processing remaining samples. An equal volume of 20µg/ml DAPI is added to each tube to achieve a final concentration of 10µg/ml DAPI prior to flow sorting with an Influx cytometer with ultraviolet excitation (Becton-Dickinson, San Jose, CA). Optimal settings for sorting FFPE samples are: Drop formation is achieved with piezzo amplitude of 6-10 volts and a drop frequency of 30khertz. The sort mode is set to purity yield with a drop delay of 31.5-32. Sheath fluid pressure is typically 17-18psi with a 100µm nozzle. For single parameter DNA content assays DAPI emission is collected at > 450nm. DNA content and cell cycle are then analyzed using the software program MultiCycle (Phoenix Flow Systems, San Diego, CA).

*DNA Extraction and Amplification:* DNA from sorted nuclei is extracted using an amended protocol for QIAamp® DNA Micro Kit from Qiagen. Briefly each sorted sample is resuspended in 180µl buffer ATL and 20µl proteinase K, and then incubated for 3 hours at 56°C for complete lysis. Samples are bound and washed according to supplier's instructions, eluted into 50µl of H2O, and then precipitated overnight with 5ul sodium acetate and 180µl 100% EtOH. Each sample is then centrifuged for 30 minutes at 20,000 x g, washed in 1ml of 70% EtOH for 30 minutes at 20,000 x g. The DNA pellet is dried then resuspended in a small volume (e.g. 10-

50µl) of H2O for final concentrations suitable for accurate quantization. Genomic DNA from sorted FFPE samples is amplified using Ovation® WGA FFPE System (NuGEN® Technologies, San Carlos CA) with an alternate fragmentation step. Resulting amplified products are used as template for aCGH. In all cases the amplification product quality is assessed by gel electrophoresis.

Array CGH: For each flow sorted tumor sample of interest we will label 1 µg of tumor DNA and 1 µg of reference DNA according to our published protocols (83). These will be hybridized to Agilent 60mer oligonucleotide CGH arrays. All microarray slides will be scanned using an Agilent 2565C DNA microarray scanner. Microarray images will be analyzed using Agilent Feature Extraction software version 11.0 (FE 11.0) using default settings according to the supplier's recommendations. Log2 ratios of fluorescent signals and corresponding log2 ratio errors, as calculated from the log10 output of FE 11.0, will be analyzed in Genome Workbench 6.7. All aCGH experiments will be evaluated using a series of quality control (QC) metrics. These include background noise, signal intensities and signal to noise ratios for each dye-specific channel, the reproducibility of a series of replicate control probes on the arrays, and a measure of the spread of the distribution of the log2 ratios reported in each experiment. The data from arrays that pass the QC metrics will then be analyzed using an aberration detection algorithm (ADM2) (84). The latter identifies all aberrant intervals in a given sample with consistently high or low log ratios based on the statistical score derived from the average normalized log ratios of all probes in the genomic interval multiplied by the square root of the number of these probes. Aberration calling thresholds for ADM2 will be determined based on hybridizations with normal 46XY and 46XX DNA derived from sorted control tissues. We will use the distribution of log2 ratios for autosome probes and the corresponding chromosome X probes from control experiments to determine the error rates in our experiments and select the statistical threshold for calling aberrant genomic intervals in the PDA samples.

NGS Template and Exome Sampling: For each sample of interest we will generate double stranded (ds) DNA template using our published methods and the Ovation® WGA FFPE System (85). Each sample selected for NGS will be assayed for final QC metrics including size range and concentration of dsDNA prior to exome sampling and sequencing. Patient matched germline DNAs will be processed in parallel. All exome sampling and NGS data generation will be done in TGen's Collaborative Sequencing Center (CSC).

NGS Analyses Workflow: Once exome sequencing data is generated, we will leverage our substantial bioinformatics and statistics skills, experience, and large-scale computational capabilities to carry out research-objective-specific customized data-analyses. We have several automated workflows that consist of both published and internally developed data analyses tools for processing sequenced data to generate interpretation-ready results. This includes germline results, such as detecting variants, comparisons with a variety of publically available variants datasets (e.g., dbSNP, 1000 genomes, etc.), functional annotation, Ti/Tv ratios, target sequencing efficiency, etc. Further, when both tumor and normal sequencing data is available, we have well-tested sophisticated workflows for somatic variant detection with detailed comparisons with publically available datasets (e.g., COSMIC). Both germline and somatic variants are comprehensively annotated for functional consequences, such as non-synonymous mutations,

frame-shift insertion-deletions. Our workflows are compatible with standard, platform-independent input sequencing data format (e.g., FASTQ format), generate detailed QC and several additional statistical metrics at various stages of data processing, and deliver results that conform to standard output formats, such as BAM (alignments), VCF (variant calls), functional annotation, etc.

HR23B protein levels will be measured by immunohistochemistry (IHC) using published protocols (86). We will use a single thin section slide for all IHC experiments. All assays will be done through TGen's Macromolecular Analyte and Processing Center (MAPC) pending additional funding. In addition a second slide from each patient will be used for further validation of the recurring t(6:9) MYB-NFIB translocation using conventional fluorescent in situ hybridization (FISH) (87). A semiquantitative analysis based upon intensity and frequency of HR23B staining and the type of dermal and epidermal infiltrate will be performed on each biopsy(87). A total staining score (TSS) will be determined out of 13, where a score of greater than or equal to 6 will be considered to be strong HR23B staining. The threshold for differentiating between positive and negative immunostaining will be set at at TSS of equal or higher than 6. This optimal cutoff was determined by the receiver operating characteristic curve (ROC) distribution analysis.

